9. ASSESSMENT SCHEDULE AND PROCEDURES

The planned schedule of procedures is shown in Table 3. Following the initial screening visit, there are 3 visits in pregnancy (early, mid and late) and 3 visits postpartum (1, 6 and 12 months). Study visits will be conducted at participating WIC clinics. Visits may also be performed at participants' homes, medical care provider offices, or other locations to maximize the opportunity of data collection for women who report difficulty in returning to the clinic. To assist with clinic visit retention, intervention staff will reach out to participants through contact outlets (e.g. telephone call, text message, Facebook group message, video conference) to remind them of upcoming clinic visits throughout the study for both the SmartMoms (Healthy Beginnings) and the Usual Care groups.

Table 3. Schedule of Procedures								
	Pregnancy					Postpartum		
		V1 Screening Early		V2 V3	V4	V5	V6	
	Screening			Mid	Late	1 month	6 months	12 months
(Weeks of gestation)	<16,0	10,0-16,6		24,0-27,6	35,0-37,6	+2,0-6,6	+22,0-25,6	+48,0-56,6
Height	X							
Weight	X	X]	X	X	X	X	X
% Fat by BIA	X	X]	X	X	X	X	X
Behavioral Run in	X]_					
			ATION					
			AI					
Blood pressure	X	X	712	X	X	X	X	X
Questionnaires		Х	ŏ		Х	X	X	X
24h diet recall	X		RANDOMIZ		X		X	X
			2					
Physical activity	X				X		X	X
(5-7 days accelerometry)								
WIC Data Abstraction					X			X
Birth Certificate Data Abstraction						X		

9.1. Visit 1

Participants will have their weight, % body fat, and blood pressure measured. Questionnaires will also be administered. After reviewing the behavioral requirements for each group with study staff, participants will be randomized to either the SmartMoms or Usual Care group. Participants will be provided with a prenatal vitamin to be taken throughout their pregnancy.

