12.3. Data Analysis Plan

Statistical analyses will be completed using SAS/STAT[®] software, Version 9.4 of the SAS System for Windows (Cary, NC, USA) by a Biostatistician. All tests will be performed with significance level α =0.05 and using intent-to-treat analysis. Outcomes will be assessed for normality (where appropriate) with the Shapiro-Wilk test. If transformed data is still not normally distributed, then non-parametric analyses will be conducted on these outcomes. LARS (least-angle regression) will be used for the covariate selection methodology. Covariates will include, but may not be limited to, the infant sex, gestational age at delivery as well as and the maternal age, weight at screening, parity, race/ethnicity, and gestational diabetes status. Treatment and BMI category will be included in all models. Intent to treat analysis will be the primary analysis type. Both completers and multiple imputation (Markov chain Monte Carlo method, preferred) may also be performed if there is a large amount (>10%) of missing data. However, we will extract the mothers' WIC record and therefore for participants who fail to return to clinic, weight measurements will be acquired from the planned chart abstraction. This should greatly decrease the amount of missing data from loss to follow-up.

Hypothesis A: Higher incidence rate of appropriate GWG

Initial results will be expressed contingency tables with incidence rate and either treatment or BMI category. Tests for associations between these variables will be based on Pearson's Chi-squared statistic. Further results will be based on a generalized linear mixed effect model with a binary distribution and a log odd link function modeling the incidence rates. The model will use random effects to account for a site effect and within-subject correlation over time. Results from this model will be reported as odds ratios of least square means, with p-values based on z-tests. Two different sets of models will be used. The first set of models will contain only treatment and BMI category, while the second is will also contain the covariates based on LARS. Pairwise post-hoc comparisons of the category variables will be corrected for multiple comparisons will be made when necessary.

Hypothesis B: Small Deviation in Weekly GWG

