2.2 Randomization

Individuals will be randomized 1:1 to either the SmartMoms® or Usual Care group. Prior to randomization, the participant and study staff will review a document that outlines behavioral requirements for each group and affirms responsibilities during the study. Once the participant confirms understanding of study requirements, randomization will occur via a phone call with intervention staff. The randomization schedule will be prepared by the study statistician and use a permuted block strategy with stratification for LDH region (1 through 9) and BMI category (normal weight, overweight, obesity) to ensure balance within each stratum between individuals in the SmartMoms® or Usual Care groups. The Research Electronic Data Capture (REDCap) will be used to conceal the allocation sequence to intervention staff until randomization occurs.

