3.3 Covariates

The models will include the following covariates: gestational age at randomization, BMI category at randomization, and parity defined categorically as nulliparous vs non-nulliparous.

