4.2 Outcomes Measures

Per the 2009 Institute of Medicine guidelines,¹ each BMI category is allocated a different rate of GWG per week, which we will base our BMI-specific definition of GWG outcomes on (Table 4).

Table 4. 2009 Institute of Medicine Guideline Ranges for Weekly GWG

BMI Category	Inadequate	Adequate	Excessive	
Normalweight	< 0.35	0.35 kg/week to 0.50	>0.50	
_	kg/week	kg/week	kg/week	
Overweight	<0.23	0.23 kg/week to 0.33	>0.33	
_	kg/week	kg/week	kg/week	
Obesity	<0.17	0.17 kg/week to 0.27	>0.27	
-	kg/week	kg/week	kg/week	

Study observed GWG is defined as the difference between clinic weight assessed during late pregnancy and clinic weight assessed during early pregnancy.

Weekly GWG is defined as study observed GWG divided by the number of weeks between the early and late pregnancy study visits, with number of weeks calculated based on the number of days between study visits divided by 7.

Incidence of appropriate study observed GWG per week is defined as the number of participants that have weekly GWG in the adequate category according to the 2009 Institute of Medicine guidelines as opposed to inadequate or excessive (Table 4).

Deviation from the 2009 Institute of Medicine guidelines will be defined as the absolute difference in weekly GWG outside of the range bounds (Table 4). Participants within the bounds will not be included in this analysis.

Adverse perinatal outcomes will be abstracted from the birth certificate records obtained from the state. The Louisiana Electronic Event Registration System (LEERS) collects all official records related to birth and includes information from prenatal and delivery records. These records will be requested from the state by the study investigators using records related to participant, incident pregnancy, and participant-reported delivery information.

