4.3 Analyses of Study Aims

Hypothesis 1: The incidence of appropriate study observed GWG per week according to the 2009 Institute of Medicine guidelines¹ will be higher in the SmartMoms® group as compared to the Usual Care group.

The categorical outcome of study-observed GWG per week attainment will be analyzed using a general linear model with a fixed effect for group (SmartMoms®, Usual Care) with a binary distribution and a log odd link function modeling the incidence rates. Covariates will include BMI category (normal weight, overweight, obesity) at randomization, parity (nulliparous, non-nulliparous), and gestational age at randomization. Results will be reported as adjusted odds ratios (OR) and/or relative risks (RR) as appropriate. The analysis will also be conducted and reported within each BMI category.

Hypothesis 2: Study observed GWG seen in the SmartMoms® group will be less as compared to the Usual Care group. This will be assessed using the following three measures: study observed GWG, weekly GWG, and deviation from the 2009 Institute of Medicine guidelines.¹

The continuous outcome of study observed GWG will be analyzed using a linear mixed-effects model including fixed effects for time (early pregnancy, late pregnancy), group, and the interaction thereof, with participant as a random effect to account for within-participant repeated measures as well as BMI category (normal weight, overweight, obesity) at randomization, parity (nulliparous, non-nulliparous), and gestational age at randomization as covariates. The continuous outcomes related to study observed GWG per week assessed only during late pregnancy (i.e., weekly GWG and deviation from the 2009 Institute of Medicine guidelines) will be analyzed analogously using a linear model with a fixed effect for group and the same covariates. The analysis will also be conducted and reported within each BMI category.

Exploratory: The incidence of adverse perinatal outcomes will be less in the SmartMoms® group as compared to the Usual Care group.

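### Within each BMI category the logistic and weekly-GWG models have no body-size covariate; adding continuous Visit 1 BMI would be a small efficiency gain at almost no cost

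*SAP*

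**What the plan says.** SAP 3.3 states: "The models will include the following covariates: gestational age at randomization, BMI category at randomization, and parity defined categorically as nulliparous vs non-nulliparous". SAP 4.3 repeats the list for Hypothesis 1 ("Covariates will include BMI category (normal weight, overweight, obesity) at randomization, parity (nulliparous, non-nulliparous), and gestational age at randomization"), applies the same covariates to the Hypothesis 2 models, and adds for both hypotheses: "The analysis will also be conducted and reported within each BMI category".

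SAP 4.2 builds every GWG outcome from the early-pregnancy clinic weight. Study observed GWG "is defined as the difference between clinic weight assessed during late pregnancy and clinic weight assessed during early pregnancy"; weekly GWG divides this by the weeks between visits, and appropriateness is judged against one fixed band per BMI category (Table 4).

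Of Visit 1, Protocol 9.1 says: "Participants will have their weight, % body fat, and blood pressure measured". Height is taken at screening (Protocol Table 3), and randomization follows Visit 1 (Protocol 8).

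Protocol 12.3 named "the maternal age, weight at screening, parity, race/ethnicity" among the covariates, with selection by least-angle regression (LARS). The May 2024 SAP amendment replaced LARS with the fixed list and left other covariates to exploratory analysis.

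**The concern.** The categories are wide. In Protocol 5.1 the obesity stratum runs from BMI 30 to 40, and Table 4 applies one band (0.17 to 0.27 kg/week) across all of it. If weekly gain varies with BMI inside a stratum, that variation stays in the residual. A chance difference in mean BMI between arms within a stratum is also left uncorrected.

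The stakes are highest in the within-BMI analyses. SAP 2.3 describes these as sufficiently powered and important for the program announcement, but with 110 women per stratum and 15% attrition each has only about 47 analysed women per arm. The total was also cut from 432 to at least 330, so there is little spare precision. A baseline covariate that is already measured is a standard way to recover some.

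**Working it through.** **1. The plan's own sample size.** Inputs from SAP 2.3 and Table 1: 28.7% vs 44.7%, α = 0.05 (two-sided assumed, as sidedness is not stated), 80% power (reading the stated β of 0.8 as power), 15% attrition.

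n per arm = [1.96·√(2·0.367·0.633) + 0.8416·√(0.287·0.713 + 0.447·0.553)]² / 0.16² = (1.336 + 0.566)² / 0.0256 = 141.3, so 142. The total is 284, and 284/0.85 = 334.1, so 335 against the stated 330. Power at 330 × 0.85 is 0.797. The figure reproduces, with no margin.

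**2. SD of weekly GWG.** The documents give none, so it is back-calculated from the stated detectable differences within BMI category at 80% power.
- SAP 2.3.1: 0.16 kg/week with 110 × 0.85/2 = 46.75 per arm. SD = 0.16/[2.80·√(2/46.75)] = 0.276.
- Protocol 12.2: 0.12 kg/week with 144 × 0.85/2 = 61.2 per arm. SD = 0.12/[2.80·√(2/61.2)] = 0.237.

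**3. Gain for weekly GWG.** Let R² be the share of within-category variance explained by continuous BMI (an assumption). SE ratio = √(1 − R²) and equivalent N = 330/(1 − R²). Stratum power uses SD 0.276 and 46.75 per arm.

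| R² | SE ratio | Equivalent N | Stratum power at 0.16 | Stratum detectable difference (kg/week) |
|---|---|---|---|---|
| 0 | 1.000 | 330 | 80.0% | 0.160 |
| 0.01 | 0.995 | 333 | 80.4% | 0.159 |
| 0.02 | 0.990 | 337 | 80.8% | 0.158 |
| 0.05 | 0.975 | 347 | 82.0% | 0.156 |
| 0.10 | 0.949 | 367 | 84.0% | 0.152 |

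**4. Is 1% to 10% reasonable?** Assume BMI is uniform within 18.5–25, 25–30 and 30–40. The mean within-category variance is V = (6.5² + 5² + 10²)/36 = 4.65. For a slope b in kg/week per BMI unit, R² = b²V/(SD² + b²V). With b = 0.01 and SD 0.276 this is 0.6%; with b = 0.03 and SD 0.237 it is 6.9%. The top of the range is therefore generous.

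**5. Cost of the extra term.** Simulation of the linear model with 47 per arm gave SE ratios of 1.005, 1.000, 0.985 and 0.959 at correlations of 0, 0.1, 0.2 and 0.3. Inside a stratum the net gain is thus about half a percentage point less than √(1 − R²) suggests.

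**6. Primary logistic endpoint.** Simulation with 280 women, 4,000 runs per row, marginal rates 28.7% vs 44.7% and one continuous covariate:

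| Covariate OR per SD | Power unadjusted | Power adjusted | SE of log OR, unadjusted → adjusted |
|---|---|---|---|
| 1.0 | 80.0% | 80.2% | 0.254 → 0.255 |
| 1.2 | 79.6% | 79.8% | 0.254 → 0.256 |
| 1.5 | 78.6% | 80.1% | 0.254 → 0.260 |
| 2.0 | 78.5% | 82.8% | 0.254 → 0.269 |

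The SE does not fall. Power rises because the log OR conditional on the covariate is larger (0.698 → 0.727 at an OR of 1.5). The gain is at most 1.5 points up to an OR of 1.5 and 4.3 points at 2.0. The within-category logistic models were not simulated.

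**7. Chance imbalance.** For BMI uniform over 30–40 the SD is 10/√12 = 2.89, and the SE of the arm difference in mean BMI is 2.89·√(2/46.75) = 0.60 units. At slopes of 0.01 to 0.03, a one-SE imbalance moves the stratum estimate by 0.006 to 0.018 kg/week. The SE of that estimate is 0.16/2.80 = 0.057, so the shift is about 0.1 to 0.3 of one SE.

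**8. The study observed GWG model.** This is a "linear mixed-effects model including fixed effects for time (early pregnancy, late pregnancy), group, and the interaction thereof, with participant as a random effect", so early weight is part of the response. In one simulated data set with a baseline imbalance, its group-by-time estimate equalled the plain change-score comparison (−2.237, SE 1.008).

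**The case against.** The strongest reply is that the list was fixed deliberately. The amendment cites advice from maternal-health statisticians, states that no study data or unblinding information were used, and keeps other covariates for exploratory work. This stands as a defence of choosing covariates in advance. It gives no reason against one prespecified continuous baseline term.

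A reader might infer that a guaranteed weight adjustment was dropped. The protocol does not support that: screening weight was subject to LARS selection, only treatment and BMI category were to be in all models, and the first model set held only those two.

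A reader might also infer that the within-BMI analyses have no control of body size at all. That goes too far. Restriction to a stratum limits body size, randomization is stratified by BMI category, and each woman's early weight is subtracted in every GWG outcome. What is missing is a covariate for any remaining relation between body size and gain.

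Nor is lost precision shown. The documents contain no within-category correlation, and at zero correlation the extra term costs slightly. For the primary endpoint, appropriate gain is a two-sided band: if higher BMI lowers excessive gain and raises inadequate gain, a linear BMI term may predict it weakly or not at all. These points reduce the size of the concern but do not remove it.

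**Conclusion.** The point holds as a modest matter of efficiency and chance imbalance. Randomization protects the comparison, adjusting for the stratified BMI category is consistent with the design, and ordinary chance imbalance is already reflected in the confidence interval. Nothing here makes the planned analysis biased or invalid.

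The benefit is mainly for weekly GWG, and it could be negligible. It rests on the assumed R² of 1% to 10%, on SDs inferred from the stated detectable differences, and on two-sided testing. For Hypothesis 1, a gain of under 2 power points assumes a covariate OR of no more than 1.5 per SD.

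The case for acting is that the downside is close to nil. Visit 1 weight is needed to compute every GWG outcome and BMI determines eligibility, so adjustment should lose no analysed woman. One limit is that Protocol 10.1 warns that some visits held outdoors under COVID-19 rules may not meet standard measuring conditions.

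**What to change.** Before the pregnancy dataset lock described in SAP 3.6, add a sentence to SAP 3.3 and carry it into 4.3. It should say that continuous Visit 1 BMI (Visit 1 weight with screening height) is included alongside BMI category in the Hypothesis 1 logistic model and the weekly-GWG linear model, overall and within each BMI category.

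Name this one variable rather than offering weight or BMI, so that no analyst choice is reopened. State that the reported odds ratio is conditional on it.

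Leave the other two GWG models unchanged. The deviation model is restricted to women outside the bounds, where the precision argument has not been shown. The study observed GWG model already holds early weight in its response.

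The cost is one degree of freedom per model and an SE increase of about 0.5% in a stratum if the correlation is zero. No new data are needed.

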3.4 Missing data

No statistical imputation of missing values will be conducted (data as observed) per contemporary guidelines.⁴

3.5 General reporting conventions

Descriptive and summary statistics will be generated for baseline characteristics and outcomes of interest. Continuous variables will be summarized using mean and standard deviation (SD). The frequency and percentages of observed levels will be reported for all categorical measures unless otherwise specified.

3.6 Timepoint of analyses

At the completion of all pregnancy visits and confirmation of infant deliveries, chart audits and data quality checks will be undertaken. Once all pregnancy data in the database is checked against the charts, the pregnancy dataset will be locked and the planned analysis to test hypotheses related to pregnancy outcomes as outlined above only will be undertaken.

4 ANALYSIS

4.1 Analysis Populations

Analyses will rely on ITT methodology. The primary analysis will use data from the visits during early and late pregnancy. For participants that had missing data at the late pregnancy time point, we will conduct a sensitivity analysis in which we use data from the visit during mid-pregnancy to calculate outcomes related to GWG per week for these individuals; that is, the incidence of appropriate study observed GWG per week according to the 2009 Institute of Medicine guidelines, as well as weekly GWG and deviation from the 2009 Institute of Medicine guidelines.¹

4.2 Outcomes Measures

Per the 2009 Institute of Medicine guidelines,¹ each BMI category is allocated a different rate of GWG per week, which we will base our BMI-specific definition of GWG outcomes on (Table 4).

Table 4. 2009 Institute of Medicine Guideline Ranges for Weekly GWG

BMI Category	Inadequate	Adequate	Excessive	
Normalweight	< 0.35	0.35 kg/week to 0.50	>0.50	
_	kg/week	kg/week	kg/week	
Overweight	<0.23	0.23 kg/week to 0.33	>0.33	
_	kg/week	kg/week	kg/week	
Obesity	<0.17	0.17 kg/week to 0.27	>0.27	
-	kg/week	kg/week	kg/week	

Study observed GWG is defined as the difference between clinic weight assessed during late pregnancy and clinic weight assessed during early pregnancy.

Weekly GWG is defined as study observed GWG divided by the number of weeks between the early and late pregnancy study visits, with number of weeks calculated based on the number of days between study visits divided by 7.

Incidence of appropriate study observed GWG per week is defined as the number of participants that have weekly GWG in the adequate category according to the 2009 Institute of Medicine guidelines as opposed to inadequate or excessive (Table 4).

Deviation from the 2009 Institute of Medicine guidelines will be defined as the absolute difference in weekly GWG outside of the range bounds (Table 4). Participants within the bounds will not be included in this analysis.

Adverse perinatal outcomes will be abstracted from the birth certificate records obtained from the state. The Louisiana Electronic Event Registration System (LEERS) collects all official records related to birth and includes information from prenatal and delivery records. These records will be requested from the state by the study investigators using records related to participant, incident pregnancy, and participant-reported delivery information.

Information will be abstracted from the LEERS records on adverse perinatal outcomes, including on the diagnosis of gestational diabetes, gestational hypertension/preeclampsia, and medically indicated Cesarean section (maternal outcomes) as well as neonatal intensive care unit admission and birth weight that will allow for calculation of small for gestational age or large for gestational age (neonatal outcomes). Specifically, we will define medically indicated Cesarean section as deliveries via Cesarean method of delivery with attempt of labor or if prior to 39 weeks with any medical indication. Small for gestational age (SGA, <10th percentile) and large for gestational age (LGA, >90th percentile) will be defined using birth weight for gestations greater than 19 weeks and less than 45 weeks based on the Alexander criteria specific for neonatal sex and rate. Preterm birth will be defined as any birth occurring prior to 37 weeks gestation; the calculation of gestational age at delivery will be determined as the difference in days between delivery date and the estimated date of conception divided by 7, with the delivery date abstracted from the birth certificate record and the date of conception calculated as 280 days prior to the participant self-reported due date.

From these outcomes, a maternal and neonatal composite will be calculated. Specifically, for each participant, the number of adverse maternal outcomes (as listed above) will be summed; from this, a binary maternal composite will be derived with any participant who has a non-zero sum indicated as having a maternal adverse outcome and those with a zero-sum having no maternal adverse outcome. A neonatal composite will be derived analogously based on the adverse neonatal outcomes (as listed above). Other study measures (e.g., baseline characteristics) are briefly defined below.

Gestational age at randomization in weeks is defined as the number of days since the date of conception divided by 7, with the date of conception calculated as 280 days prior to the participant self-reported due date.

Parity is defined categorically as either nulliparous or non-nulliparous based on participant self-report.

Race/ethnicity is based on self-report and includes the options 'Hispanic' (if participant reports any Hispanic, Latino/a, or Spanish origin), 'Non-Hispanic White' (if participant reports no Hispanic ethnicity and indicates White race), 'Non-Hispanic Black' (if participant reports no Hispanic ethnicity and indicates Black or African American race), and 'Mixed or Other' (if participant reports multiple races or ethnicities, or a race other than White or Black).

Marital status is defined based on self-report and includes options 'Married/Living with Significant Other' (if participant reports to be married or living with significant other) or 'Not Married' (if participant reports not to be married, or to be separated, divorced, or widowed).

Educational attainment is defined based on self-report and includes options 'Some college education' (if participant reports a college degree, postgraduate work, or 1-3 years of college, business, or technical school) or 'No college education' (if participant reports some high school or a high school diploma or GED).

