11.2.1. Adverse Events

An **adverse event (AE)** is defined as any untoward medical occurrence which may or may not be associated with participation in the study, including but not limited to:

- A clinically significant new diagnosis or medical problem reported by the participant.
- An event that requires a non-routine visit to a medical care provider.
- An event that occurs as a result of a study procedure.
- Unanticipated untoward medical events that are not plausibly pregnancy related but may or may not be study related

A **serious adverse event (SAE)** is defined as an untoward medical occurrence, whether associated with study participation or not, that results in one of the following:

- Death: maternal death and/or fetal death, including miscarriage, therapeutic abortion because of increasing signs of maternal or fetal compromise, and stillbirth
- Life-threatening event: Life threatening events in the mother or fetus are defined as those that in the view of the research staff and PI put the individual participant at imminent substantial risk of dying, or if continued participation in the study might have resulted in death.
- Hospitalization (initial or prolonged): Maternal hospitalization or acute outpatient evaluation (e.g. in an emergency room or labor and delivery triage unit) alone is not sufficient to qualify as a serious adverse event. Hospitalization or acute outpatient evaluation for the following would not be considered a serious adverse event: term delivery, preterm premature rupture of membranes (pPROM), pyelonephritis, bedrest, contractions, ruling in or out preeclampsia, and preterm labor. Any medical or surgical procedure performed (e.g., surgery, transfusion) itself is not the adverse event; instead, the condition that leads to the procedure is the adverse event.
- Preterm delivery prior to 32 weeks gestation
- Disability or permanent damage: If the adverse event resulted in a substantial disruption of the mother's ability to conduct normal life functions, i.e., the adverse event resulted in a significant, persistent or

permanent change, impairment, damage or disruption in the participant's body function/structure, physical activities and/or quality of life. The recommendation for bedrest does not constitute an SAE.

- Medical Intervention to prevent permanent impairment or damage

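### The exploratory neonatal composite has no death component, so a fetal or neonatal loss that meets no listed component is coded event-free or drops out

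*SAP*

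**What the plan says.** SAP 4.2 takes its perinatal data from one source: "Adverse perinatal outcomes will be abstracted from the birth certificate records obtained from the state". The neonatal items are "neonatal intensive care unit admission and birth weight that will allow for calculation of small for gestational age or large for gestational age (neonatal outcomes"). The maternal items are "diagnosis of gestational diabetes, gestational hypertension/preeclampsia, and medically indicated Cesarean section (maternal outcomes").

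The same section then defines preterm birth and goes on to say that the composites are calculated from these outcomes. The coding rule is spelled out for the maternal composite: the component count is summed, any non-zero sum is an event, and the rest are coded as "those with a zero-sum having no maternal adverse outcome". The neonatal composite takes over this rule by reference: "A neonatal composite will be derived analogously based on the adverse neonatal outcomes (as listed above").

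Small and large for gestational age are defined "using birth weight for gestations greater than 19 weeks and less than 45 weeks".

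On missing values, SAP 3.4 says: "No statistical imputation of missing values will be conducted (data as observed"). SAP 4.3 analyses adverse perinatal outcomes with a binary log-odds model, under the exploratory hypothesis that they are less frequent with SmartMoms. SAP 1.5 classes pregnancy and birth outcomes as exploratory.

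Protocol 11.2.1 counts as a serious adverse event "Death: maternal death and/or fetal death, including miscarriage", and goes on to name therapeutic abortion for maternal or fetal compromise and stillbirth. Nothing in either document connects those records to the composites.

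**The concern.** A composite of neonatal harm should not improve when a pregnancy is lost. Here the worst outcome is not a component, and everything that is not a listed component adds up to no event. Randomization follows Visit 1, at 10 to 16 completed weeks (Protocol 8 and Table 3), so miscarriage and stillbirth can occur afterwards in either arm.

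What is at stake is the direction of an exploratory comparison that readers may use to judge safety. The intervention restrains weight gain, and Protocol 11.2.3 sets weight-loss alerts for it. If losses were more frequent in one arm, that arm's neonatal composite would be flattered. Removing losses that lack a birth record would also sit badly with the intent-to-treat approach in SAP 4.1.

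**Working it through.** The plan gives no event rate, power or sample size for the composites, so there is no figure to reproduce. The check has two parts.

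**1. How the rule treats a loss**

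| Type of loss | Small/large for gestational age | Intensive-care admission | Result under SAP 4.2 and 3.4 |
|---|---|---|---|
| Loss at 19 weeks or earlier, birth record exists | Outside the definition window | None | Sum is zero, so no event, if undefined items count as absent; otherwise missing |
| Later stillbirth, record exists, weight neither small nor large | No | None | Sum is zero, so no event |
| Stillbirth with a recorded small weight | Yes | None | Event, through weight only |
| Neonatal death after intensive-care admission | Depends on weight | Yes | Event, through admission only |
| Neonatal death without admission, weight neither small nor large | No | No | Sum is zero, so no event |
| Any loss without a birth record | Not observed | Not observed | Missing and not imputed, so it drops out |

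If preterm birth is a component, recorded losses before 37 weeks could also score as events, provided a loss is treated as a birth. Losses at 37 weeks or later, and losses without a record, would still be handled as in the table.

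**2. How many women, and how far the comparison moves**

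Inputs: N = 330, randomized 1:1 (SAP 2.1 and 2.2), so 165 per arm. The loss rate r is an assumption.

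Expected losses = N × r, and P(at least one) = 1 − (1 − r)^330:
- r = 0.5%: 330 × 0.005 = 1.65; probability 81%
- r = 1%: 330 × 0.01 = 3.3; probability 96%
- r = 2%: 330 × 0.02 = 6.6; probability 99.9%

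So about 2 to 7 women, and very likely at least one.

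To show the direction, assume a 30% composite rate among survivors in both arms, losses of 1% in Usual Care and 3% in SmartMoms (2% overall), and no loss meeting a listed component.
- Death counted as an event: Usual Care 0.99 × 0.30 + 0.01 = 30.7%; SmartMoms 0.97 × 0.30 + 0.03 = 32.1%; difference +1.4 points.
- Losses scored zero: 0.99 × 0.30 = 29.7% and 0.97 × 0.30 = 29.1%; difference −0.6 points.
- Losses dropped: 30% and 30%; difference 0.

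With survivor rates of 20% and 40% in place of 30%, the difference with death counted is +1.6 and +1.2 points, and with losses scored zero it is −0.4 and −0.8. The sign reverses in each case. The error is the difference in loss rates (2.0 points) when losses score zero, and that difference times the proportion of survivors without an event (2.0 × 0.70 = 1.4 points) when they are dropped. With equal loss rates in the two arms, the difference is 0 under all three scorings.

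**The case against.** The case for leaving the rule alone has several parts.

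- **The SAP does not say that an unobserved component counts as zero.** Since missing values stay missing, a miscarriage with no birth record is most naturally missing. This stands: such a loss is dropped, not called a success. It does not help a recorded loss with every component absent. Which losses have a record in the state system cannot be learned from the documents.
- **Some deaths are caught.** Admission before death, a recorded small weight, or possibly preterm birth would each make the loss an event. This stands and reduces the number affected.
- **The outcome is exploratory.** SAP 3 says exploratory results should not be used to infer definitive treatment effects, and fetal losses still reach safety review under Protocol 11.2. This stands and limits the consequence. It does not justify an outcome that can move in the wrong direction.
- **Whether a morbidity composite should include death is partly a design choice.** That is fair, but the plan then needs to say how losses are handled, and it does not.

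A reader might infer three stronger things that the documents do not support.

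1. That the maternal composite also misclassifies early losses. A woman whose pregnancy ends before she develops gestational diabetes or has a Cesarean did not have those outcomes. That is a competing risk, not a wrong code.
2. That neonatal deaths are already held as serious adverse events. The death criterion in Protocol 11.2.1 names the mother and the fetus; death of a live-born infant is not listed.
3. That the composite could be out by 4 points in an arm. Seven losses in one arm would be 7/165 = 4.2 points, but this needs the top of the assumed range, no loss meeting any component, and all seven in the same arm. With no true arm difference, the chance of that split is about 2 × 0.5^7 = 1.6%.

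**Conclusion.** The point holds for the neonatal composite. Death is not a component, a zero sum means no event, and no other section repairs this. The size is small: about 2 to 7 of 330 women at an assumed 0.5% to 2% loss rate, fewer where a loss also meets a listed component. In the illustration, with a threefold difference in loss between arms, the error is 1.4 to 2.0 points, enough to reverse the sign of a small difference. The loss rates and the 30% survivor rate are assumptions; the documents give neither. The primary weight-gain analysis does not use this composite. The change is worth making because it is cheap and removes a rule that can favor the arm with more losses, not because a trial conclusion depends on it.

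**What to change.** Amend SAP 4.2 as follows:

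- Add fetal death and neonatal death to the neonatal composite and count either as an event.
- Take fetal death from the serious adverse event records under Protocol 11.2.1, including where no birth record exists. Name a source for neonatal death, which that section does not list.
- Keep randomized pregnancies that end in loss in the neonatal denominator.
- Code event-free only when every component has been observed.
- State whether preterm birth is a component of the neonatal composite.
- Report fetal and neonatal losses by arm beside both composites.

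The cost is SAP wording, a link to the adverse event data, and a source for neonatal deaths. The downside is a slightly more heterogeneous composite that mixes rare deaths with more common morbidity; the by-arm table of losses lets readers separate the two.
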